1 RATIONALE FOR THE STUDY

Patients with brain tumor-related epilepsy (BTRE) present a complex therapeutic profile and require a unique and multidisciplinary approach. There are many factors to take into consideration, especially the management of epilepsy, which is often considered the most important risk factor for long-term disability (Maschio, 2012).

In patients with brain tumors, seizures are the onset symptom in 20-40% of patients, while a further 20-45% of patients will present with seizures during the course of the disease. Overall, the incidence of epilepsy in brain tumors, regardless of histological type and anatomical site of the lesion, varies from 35 to 70% (Rossetti and Stupp, 2010; Vecht and Wilms, 2010; Singh et al, 2007; Hildebrand et al, 2005; Wen and Marks, 2002; Glantz et al, 2000).

Lacosamide (LCM, VIMPAT[®]) is an antiepileptic drug (AED), which has been shown to provide a favorable benefit-risk profile and was approved by the European Medicine Agency (EMA) on 29 Aug 2008 (EU/1/08/470/01 to 013 and EU/1/08/470/016 to 023; EMA reference EMEA/H/C/000863) as adjunctive therapy in the treatment of partial-onset seizures with or without secondary generalization in patients with epilepsy aged 16 years and older (film-coated tablets of 50mg, 100mg, 150mg, and 200mg, syrup of 10mg/mL, and solution for infusion of 10mg/mL). In addition to the European Union, LCM is approved as adjunctive therapy in adults suffering from partial-onset seizures in at least 38 other countries to date. In the United States, LCM is approved as adjunctive therapy or monotherapy in patients age 17 years and older and suffering from partial-onset seizures.

The pharmacokinetic profile of LCM includes minimal cytochrome P450 interaction and low (<15%) protein binding, resulting in a low risk for drug-drug interaction (Lacosamide Summary of Product Characteristics, 2011). This is particularly important in the context of BTRE, since many chemotherapeutic agents are susceptible to metabolism via the P450 pathway, as are a number of AEDs which may be co-prescribed during the natural history of disease.

Lacosamide has been shown to be efficacious and generally well tolerated in real life clinical practice, from first adjunct to later treatment lines (Stephen et al, 2011; Villanueva et al, 2012).

The first noninterventional study (NIS) evaluating the use, effectiveness, and tolerability of LCM in routine clinical practice (VImpaT added to One Baseline AED, VITOBA, ClinicalTrials.gov NCT01098162) started in Germany in May 2009 in about 550 patients with less difficult-to-treat disease, excluding a complex therapeutic profile like patients with BTRE, and being treated with only a single Baseline AED. The Observation Period per patient in the VITOBA study was 6 months. The results of the second interim analysis based on >300 patients indicate improved seizure control with a favorable safety and tolerability profile when LCM is used as adjunctive treatment to AED monotherapy in routine clinical practice (Noack-Rink et al, 2012).

There are limited data available in patients with complex-to-treat diseases like BTRE, as well as limited established guidance. However, general consensus is that nonenzyme inducing AEDs, like LCM, should be preferred because chemotherapy and steroids are the main treatment in this population, and both are affected by enzyme inducers.

The most important published uses of LCM in this population are a retrospective analysis including 70 patients in 5 US centers (Saria et al, 2013) and prospective case series including

14 patients in Italy (Maschio et al, 2011), both of which show good tolerability and effectiveness of LCM in this subpopulation.

To better evaluate the use of LCM in patients with BTRE in routine clinical practice, a new observational study is necessary. The present study (EP0045) will significantly add to the published experience, and hopefully lead to the possibility of informed design of comparative studies, which is currently not possible due to the paucity of data in this area.

EP0045 is a multicenter, prospective NIS conducted at specialized sites in approximately 6 European countries, with a 6-month Observation Period. Lacosamide will be added to any AED therapy (1 or 2 AEDs) in approximately 100 patients with BTRE.

The primary objective of this study is to evaluate in routine clinical practice the effectiveness of LCM added to 1 or 2 AEDs in the treatment of patients with BTRE due to low-grade glioma. The secondary objective of this study is to evaluate the tolerability and quality of life (QoL) of patients with BTRE due to low-grade primary brain tumor who are treated with LCM added to 1 or 2 AEDs.

This observational study is entirely noninterventional. Patients will receive their usual medical care, which may include but is not limited to diagnostic or therapeutic procedures and medical treatment. The decision for initiating LCM therapy will be independent of study participation.

The patient (or legal representative) will be required to provide written informed consent for the use of his/her medical data before enrolling in the study.

2 STUDY TYPE

EP0045 is a multicenter NIS conducted at specialized sites in approximately 6 European countries.

3 STUDY OBJECTIVES

The primary objective of this study is to evaluate the effectiveness and patient global impression of LCM added to 1 or 2 AEDs in the treatment of patients with BTRE due to low-grade primary brain tumor.

The secondary objective of this study is to evaluate the tolerability and QoL of patients with BTRE due to low-grade primary brain tumor who are treated with LCM added to 1 or 2 AEDs.

4 STUDY VARIABLES

4.1 Primary variables

The following primary variables will be measured:

- Response at the end of the 6-month Observation Period, where a responder is a patient experiencing a 50% or greater reduction in partial-onset seizure frequency from Visit 1 (Baseline) to Visit 3 (Month 6 or end of Observation Period)
- Patient Global Impression of Change (PGIC) rating at Visit 3 (Month 6 or end of Observation Period)

4.2 Secondary variables

The following secondary variables will be measured:

- Retention on LCM at the end of the 6-month Observation Period
- Time to discontinuation of LCM treatment from the date of first dose of LCM
- Change from Visit 1 (Baseline) to Visit 3 (Month 6 or end of Observation Period) in the 5-Level EuroQol-5 Dimension Quality of Life Assessment (EQ-5D-5L) visual analogue scale (VAS) score and change in utility as converted from the 5 dimensions
- Change from Visit 1 (Baseline) to Visit 3 (Month 6 or end of Observation Period) in the M.D. Anderson Symptom Inventory - Brain Tumor (MDASI-BT)
- Actual change from Visit 1 (Baseline) to Visit 3 (Month 6 or end of Observation Period) in seizure frequency (seizures per 28 days)
- Percentage change from Baseline in seizure frequency
- Seizure-free status (Yes/No) at the end of the 6-month Observational Period
- Discontinuation rate of LCM due to adverse drug reactions (ADRs)
- Discontinuation rate of LCM due to lack of effectiveness
- Clinical Global Impression of Change (CGIC) rating at Visit 3 (Month 6 or end of Observation Period)

4.3 Safety variables

The following safety variables will be collected:

- Occurrence of ADRs or adverse events of special interest (AESIs) spontaneously reported by the patient or observed by the treating physician
- Patient withdrawal due to ADRs

5 STUDY DESIGN

EP0045 is a multicenter, prospective, single-arm NIS conducted at specialized sites utilizing LCM added to existing treatment with 1 or 2 Baseline AEDs in patients ≥ 16 years of age with BTRE secondary to low-grade tumor. There are expected to be approximately 100 patients enrolled in the study (see Section 11.5).

The patients will be followed as per current clinical practice for their condition. No additional diagnostic or monitoring procedures will be applied. The choices of AED treatment are made independently by the treating physician in the regular course of practice and are, therefore, independent of participation in this NIS.

The observation of the first patient will start after a positive opinion to conduct the study has been received by the responsible ethics committee(s) (Section 12.4.2) and the regulatory authority(ies) if applicable (Section 12.4.3).

Eligible patients will be enrolled consecutively and all patients (and/or their parents or legal representatives) have to accept in writing that his/her medical data will be used for the evaluation of the study results by signing a study-specific Patient Data Consent form according to local requirements.

The clinical evaluation of patients with BTRE secondary to low-grade tumor will be performed by the treating physician following routine clinical practice. All visits and assessments will be scheduled and conducted per routine clinical practice. It is anticipated that visits will occur every 3 months based on standard of care; therefore, each patient will have approximately 3 visits during their participation in this study. These visits will consist of:

- Visit 1, Baseline
- Visit 2, approximately 3 months after Baseline according to routine practice
- Visit 3, approximately 6 months after Baseline according to routine practice or end of Observation Period

Patients who discontinue early should perform Visit 3 assessments as a Withdrawal Visit.

All data to be collected at Visits 1, 2, and 3 are described in Section 15, Table 15-1 (to be collected as available). The management and reporting of ADRs and AESIs will be handled according to international drug safety regulations and UCB procedures.

Documentation of all study assessments is to be performed by the treating physician in the study-specific electronic Documentation form (eDF). Although the study is noninterventional in nature, every attempt must be made to assess all participating patients in the same way.

6 EXPECTED STUDY DURATION

The planned number of patients is 100 (see Section 11.5), with 93 evaluable patients expected. Approximately 25 specialized centers are planned for participation. The expected recruitment period is 12 months.

The Observation Period per patient will be up to 6 months after initiation of LCM treatment.

7 ANTICIPATED REGIONS AND COUNTRIES

The study will be conducted in approximately 6 European countries (France, Germany, Italy, Netherlands, Spain, United Kingdom) with possible extension to other countries.

8 SELECTION AND WITHDRAWAL OF PATIENTS

8.1 Selection criteria

Before any data are collected for any patient in this NIS, written data consent will be properly executed and documented.

The following selection criteria must be followed for patients entering the NIS:

1. Patient has never been treated with LCM prior to this NIS or treatment with LCM for the first time started no earlier than 7 days prior to enrollment in this NIS.
2. The decision by the treating physician to prescribe LCM falls within current standard clinical practice, and the treatment decision is clearly separated from the decision to consider inclusion of the patient in the NIS.
3. A Patient Data Consent form is signed and dated by the patient and/or by the parent(s) or legal representative.
4. Patient is a male or female ≥ 16 years of age.

5. Patient must have a diagnosis of BTRE secondary to low-grade glioma (World Health Organization Grade 1 to 2 at time of enrollment).
6. Patient has a retrospective Baseline seizure frequency of at least 1 partial-onset seizure in the 8 weeks prior to start of LCM treatment.
7. Patient does not have a previous diagnosis of epilepsy before tumor onset.
8. Patient does not have brain metastases.
9. Patient has a Karnofsky performance status scale index $\geq 60\%$.
10. Patient is currently taking only 1 or 2 Baseline AEDs for epilepsy other than LCM.
11. Patient has received a maximum of 4 different lifetime AEDs ever before entering the NIS.

8.2 Withdrawal criteria

Patients are free to withdraw from the study at any time, without prejudice to their continued care.

Physicians are free to add or withdraw any medication or to withdraw the patient from the study at their own discretion.

If a patient needs to increase the dose of the Baseline AEDs (1 or 2) or needs to be treated with more than 2 AEDs other than LCM, these changes can be implemented, but the patient will be withdrawn from the study.

If the physician elects to stop LCM treatment, the patient will be withdrawn from the study.

The primary reason for withdrawal must be documented in the patient's eDF. When the primary reason for withdrawal is an ADR, the ADR must be reported as described in Section [10.1.7](#).

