3.5.3 Full Analysis Set

The Full Analysis Set (FAS) is defined as all patients in the SS who have at least 1 post-Baseline PGIC or seizure assessment. The FAS will be used for the analysis of the primary and most secondary variables including any subgroup analyses. In addition, demographic and baseline summaries will be based on the FAS.

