8.1.1 Derivations of primary efficacy variables

8.1.1.1 Seizure frequency response

A responder is defined as a patient who experiences a 50% or greater reduction in partial-onset seizure frequency from Visit 1 (Baseline) to Visit 3 (Month 6 or end of Observation Period).

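### A patient can start a new AED, stay in the study and be scored as a responder, because neither protocol 8.2 nor the SAP responder rule addresses that change

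*Protocol*

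**What the plan says.** Protocol section 5 describes a single-arm study "utilizing LCM added to existing treatment with 1 or 2 Baseline AEDs". Selection criterion 10 (protocol 8.1) admits patients on either number: "Patient is currently taking only 1 or 2 Baseline AEDs for epilepsy other than LCM".

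Protocol 8.2 names two AED changes that end participation. One is a rise in the dose of a Baseline AED. The other is that the patient "needs to be treated with more than 2 AEDs other than LCM". For both, "these changes can be implemented, but the patient will be withdrawn from the study". The same section states that "Physicians are free to add or withdraw any medication".

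SAP 8.1.1.1 defines the seizure endpoint: "A responder is defined as a patient who experiences a 50% or greater reduction in partial-onset seizure frequency", measured from Visit 1 to Visit 3. The definition says nothing about other AEDs. The Full Analysis Set (SAP 3.5.3) is "all patients in the SS who have at least 1 post-Baseline PGIC or seizure assessment".

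**The concern.** The design describes lacosamide joining an AED regimen that is already in place. The withdrawal rule protects that only in part: it acts on a higher dose of a Baseline AED and on a third non-LCM AED, but not on every new AED. The responder definition does not close the gap. A fall in seizures after a newly started AED is therefore tabulated as a response in a study of lacosamide added to existing treatment, and the reader cannot see how many such responses there are. PGIC at Visit 3, the other primary variable, has the same exposure.

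What is at stake is how the primary responder percentage is read. The sample size and the conduct of the main analysis are not affected.

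**Working it through.** **Who is withdrawn.** The inputs are the entry count of 1 or 2 AEDs (protocol 8.1, criterion 10) and the two triggers in protocol 8.2.

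- Enters on 1, starts another: 1 + 1 = 2, which is not more than 2. Stays.
- Enters on 2, starts a third: 2 + 1 = 3. Withdrawn.
- Enters on 2, replaces one with a new AED: 2 − 1 + 1 = 2. Stays, provided the old and new AEDs do not overlap to make 3.
- Any Baseline AED dose increase: withdrawn.

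**Whether the analysis separates these patients.**

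- The Full Analysis Set has no exclusion for an added AED. The modified FAS (SAP 3.5.4) excludes on lacosamide dose only.
- There is no Per-Protocol Set (SAP 3.4) and no covariate adjustment (SAP 4.1).
- The Core AED subgroups (SAP 4.8, 6.4) rest on AEDs taken at Baseline.
- The concomitant medication summary (SAP 6.4) combines drugs started before, on and after the first lacosamide dose, and does not link them to response.

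**Which interval is scored.** SAP 3.10.4 computes seizures × 28/D. D is 56 days at Baseline and, afterwards, the days since the previous visit. At the nominal visit days in SAP 3.2.1 (90 and 180), D for Visit 3 is 180 − 90 = 90 days. If a second AED is started at Visit 2, all 90 scored days are on it, and the first 90 days, on lacosamide plus the original AED, do not enter the endpoint.

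**The plan's precision figure (protocol 11.5).** n = 1.96² × 0.60 × 0.40 / 0.10² = 92.2, rounded up to 93. The half-width at 93 is 1.96 × √(0.24/93) = 0.0996. The stated 93 and 0.10 reproduce. The 7% loss implied by 93 of 100 also fits: 93/(1 − 0.07) = 100.

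**Illustration.** The share of patients who change AEDs is not in the documents, so 5%, 10% and 20% of 93 (5, 9 and 19 patients) are assumptions. Start from 56/93 = 60.2% (Clopper-Pearson 49.5% to 70.2%). Let r be the number of responders among those who changed. The supportive rate is (56 − r)/93. The low end of r is about 30% of those who changed, and the high end is all of them.

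| Changed | r | Supportive rate | Shift (r/93, points) |
|---|---|---|---|
| 5 | 2 to 5 | 58.1% to 54.8% | 2.2 to 5.4 |
| 9 | 3 to 9 | 57.0% to 50.5% | 3.2 to 9.7 |
| 19 | 6 to 19 | 53.8% to 39.8% | 6.5 to 20.4 |

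Now drop the same patients from numerator and denominator instead, assuming they respond at about 60%:

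- (56 − 3)/(93 − 5) = 60.2%
- (56 − 5)/(93 − 9) = 60.7%
- (56 − 11)/(93 − 19) = 60.8%

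The rate barely moves. The shifts in the table come from the counting rule and do not measure bias.

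**The case against.** The strongest reply is that this is a noninterventional, single-arm study of routine practice with no inferential analysis. Without a control arm no individual response is causally assigned to lacosamide, and tumor treatment may change during follow-up as well. Counting outcomes regardless of permitted co-medication is a legitimate choice. The objective in protocol section 3 refers to lacosamide added to 1 or 2 AEDs, and a patient who moves from 1 to 2 still fits that description. Concomitant AEDs and efficacy data are listed, so the patients could be found by hand.

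Much of this stands, and it is why the primary analysis should stay as it is. It does not dispose of the point. Protocol 8.2 already departs from following patients whatever happens to their AEDs, because it withdraws them for two kinds of change. Section 5 and SAP 2.3 describe the regimen as existing treatment. Listings do not give a reader the number of responders affected.

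Four stronger readings are tempting, and the documents do not support them:

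- **That the responder rate is inflated by a known amount, perhaps more than the ±10 points.** No frequency is given, and some of these patients might have responded on lacosamide without the new AED.
- **That adding an AED and raising a Baseline dose are equivalent.** No section says so; this would be a clinical judgement.
- **That only patients entering on 1 AED are concerned.** The swap in a patient on 2 AEDs is also untouched.
- **That a dose increase removes the patient from the analysis.** It ends participation, but data are analyzed up to the last visit attended (SAP 4), and a withdrawal visit more than 135 days after Visit 1 falls in the Visit 3 window (SAP 3.2.1) and can be scored as a response. For earlier withdrawal visits the SAP is unclear: the day rule points to Visit 2, while the Visit 3 label also names the Withdrawal Visit.

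**Conclusion.** The point holds as an interpretive gap in the primary responder rate and the Visit 3 PGIC. A new AED can be started without withdrawal, and the plan neither conditions on it nor counts it. The protocol does not contradict itself here: 8.2 sets two different triggers, and together they do not fully secure the existing-treatment design in section 5.

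The size of any bias cannot be derived from the documents. The table shows only how sensitive the rate would be under assumed shares, with every affected patient having Visit 3 data and counted in the 93. At about 10% of patients changing, the largest shift (9.7 points) is close to the planned half-width. That is a reason to report the number and says nothing about its likely value. If no patient changed, the concern closes. A supportive analysis should be added; the sample size does not change.

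**What to change.** Leave the primary analysis unchanged. In SAP 8.1.2.1, add a supportive responder analysis for the FAS in which a patient counts as a non-responder if, after the first lacosamide dose and before the Visit 3 assessment, the patient starts a new non-LCM AED or has a Baseline AED dose increase. Treating both changes alike matters, because patients withdrawn for a dose increase can otherwise still be scored as responders. Report the number of patients affected, and give the same count alongside PGIC in SAP 8.1.2.2.

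The SAP should also settle three details in advance:

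- **Denominator:** how flagged patients without a Visit 3 frequency are handled, since the main analysis uses only patients with available data.
- **Partial dates:** SAP 4.2.1 moves a start date that lacks its day to the first lacosamide day when the month and year match, so a later start could escape the flag.
- **Brief courses:** as worded, any new start counts.

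The cost is one derived flag and one extra row. AEDs are scheduled for recording at all three visits (protocol Table 15-1); that doses are recorded in enough detail is an assumption. The supportive rate will be conservative, because some flagged patients might have responded anyway.

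The sponsor should reconcile the two triggers in protocol 8.2 with the design statement in section 5. No clinical rule is proposed.

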9 STUDY TREATMENT(S)

Patients will be treated with commercially available LCM and with commercially available AEDs, as prescribed by treating physicians, in accordance with current clinical practice.

9.1 Numbering of patients

Each patient will receive a unique 5-digit number assigned when entering the study that serves as the patient identifier throughout the study.

The patient identification list will be kept by the treating physician. Access to this list may be granted only to members of staff, authorized persons of UCB (or designees), and the competent authorities. The study monitor is also bound to confidentiality. After the end of the study, the identification list will remain with the physician.

10 ASSESSMENT OF SAFETY

For the assessment of safety of LCM, the causal relationship, seriousness, and outcome of ADRs and AESIs will be collected during the Observation Period. It is the task of the treating physician to make a judgment about a causal relationship with the LCM intake.

10.1 Adverse events and adverse drug reactions

10.1.1 Definitions of adverse events and adverse drug reactions

An adverse event (AE) is any untoward medical occurrence in a patient or clinical investigation patient administered a pharmaceutical product which does not necessarily have a causal relationship with this treatment. An AE can therefore be any unfavorable and unintended sign (including an abnormal laboratory finding), symptom, or disease temporally associated with the use of a medicinal product, whether or not related to the medicinal product.

An ADR is a response to a medicinal product which is noxious and not intended. This includes adverse reactions which arise from:

- The use of a medicinal product within the terms of the marketing authorization;
- The use outside the terms of the marketing authorization, including overdose, off-label use, misuse, abuse, and medication errors; and
- Occupational exposure (this refers to the exposure to a medicinal product as a result of one's professional or nonprofessional occupation)

